Comparative effectiveness of energy doses in critical illness

Short title: The Energy Dose Study

Principal Investigator: [name].

Protocol Version Date: 6/2/2014

NCT Number: NCT01369147

Abstract:

Protein and/or energy deficits are associated with increased rates of hospital infection, skeletal muscle weakness, impaired wound healing, and prolonged convalescence in ICU patients. To prevent or treat malnutrition, enteral nutrition (EN) and/or parenteral nutrition (PN) are routinely given worldwide to a significant proportion of ICU patients. Optimal caloric requirements in critically ill patients are unknown due to a lack of rigorous randomized clinical trials. The comparative efficacy of energy doses in critically ill patients is unknown and clinical recommendations are conflicting and controversial; this issue is the focus of our study.

We have designed this pilot, single-center Randomized Clinical Trial (RCT) to prospectively compare, for the first time, the clinical efficacy of different energy doses in ICU patients requiring PN due to intestinal failure/dysfunction. A total of 60 patients will be studied (20 per energy dose group) to generate critical preliminary data needed to inform subsequent appropriately powered Phase III multicenter trials.

The primary aim of this study is to perform a controlled, double-blind, prospective, randomized, intent-to-treat Phase II clinical trial to test the efficacy of three specific energy doses [0.6, 1.0 and 1.3 x measured REE (resting energy expenditure), respectively], given for 28 consecutive days during the ICU course, on 28-day total hospital-acquired infections (primary endpoint), Blood Stream Infections (BSI), and other important clinical outcomes in medical/surgical ICU patients requiring specialized parenteral \pm enteral feeding. We would also determine, in these subjects A) the impact of cumulative and mean daily 28-day energy deficits [energy intake-measured REE] on clinical outcome endpoints; and B) the practical utility of estimated REE determined by Harris-Benedict equation versus measured REE across different energy doses. We would also like to determine the impact of administered energy dose and energy deficits on global metabolomic patterns over time and their association with key clinical outcomes.

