- C) Blood sampling for metabolomics analysis (Aim 3): Baseline and serial study blood for processing as below will be drawn between 0800 and 1000 h. at the baseline day and study days 3, 7, 14, 21 and 28. A total of 28 mL of blood will be drawn at baseline and days 7, 14, 21 and 28 of study. A total of approximately 150 mL of blood will be obtained for analysis during the first 28 days after entry.
- D) Assessment and monitoring of blood glucose concentrations: Three blood glucose data points (the initial AM blood glucose sent to the hospital laboratory, and one representative laboratory or fingerstick blood glucose level obtained at a time point between 1400-1660 h and again between 2200-2400 h) \pm 1 hour window.
- E) Assessment and monitoring of nosocomial infections: New hospital infections will be diagnosed based on standardized CDC criteria exactly as currently performed in [name] multicenter NIH U01 study (updated by CDC in 2009). All infections will be adjudicated by review of pertinent data in a blinded fashion by Infectious Disease Co-I [name].
- F) Stool sampling for microbiome analysis (Aim 3): Stool samples, when available, will be collected by the primary nurse at baseline and study days 3, 7, and 14, within 24 hours of the specific study day. The sample will be placed in a vial and frozen for later analysis by colleagues at the University of Chicago. The date, time, and consistency of stool will be collected for each sample.
- G) Handgrip strength test for overall strength assessment (Aim 3): If patients are deemed alert and able by study team, a Jamar Hydraulic Hand Dynamometer (Sammons Preston Rolyan, Chicago, IL) will be used to measure handgrip strength on the day subjects leave the ICU, then 3 and 7 days after ICU discharge. If the subject is consented before surgery and subsequent ICU admission, a handgrip measurement will be taken during pre-op. At each time point, the subject will be asked to squeeze the handheld dynamometer as hard as they can for 3 seconds, and they will be asked to repeat this 3 times, with a 1-minute rest between measurements.

Serial data entry via case report forms (CRFs): The investigators will monitor all study subjects daily during the ICU stay and after discharge to the general ward and enter data into

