High-resolution metabolomics analysis: Plasma samples will be obtained at baseline and on days 3, 7, 14, 21 and 28 after entry (please see study schema above). Metabolomic profiles at the specific analysis time-points will be compared to compare subjects: 1) within the three study energy doses; 2) whom develop a nosocomial infection or a BSI versus those who do not; and 3) who die compared to those who are alive at 28 days. Samples will be analyzed in triplicate with a Thermo LTQ-Velos Orbitrap high-resolution mass spectrometer (\geq 50,000 resolution) following extraction with acetonitrile containing an internal standard mixture and separation on anion exchange and C18 columns. Validated extraction methods (apLCMS and xMSanalyzer) ^{44, 62} will be used to provide a mass/charge ratio (m/z) feature table of detected ions, characterized by relative retention time and accurate mass. The mass spectrometer will be set to collect data from m/z ratio 85 to 2000 daltons over a 10-minute chromatography period. Internal stable isotopic standards are spiked into every sample so that the relative retention time and accurate mass provide unambiguous denotation of an ion even if the chemical is unidentified ⁶³; relevant reference samples are included preceding and following each block of 20 samples for long-term quality assurance. Electrospray ionization will be used in the positive ion mode for detection. When necessary, tandem mass spectrometry will be used to positively identify metabolites of interest, with a metabolite defined as any chemical in a biological system.

Stool sampling and gut microbiome analysis: On study days 0, 3, 7, and 14 the primary nurse will collect a small sample of stool (\pm 24-hr window of each study day). All specimens will be collected into sterile containers, processed, and stored at -80°C as previously outlined ⁶⁴. The

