Twenty-eight day mortality will be summarized as a proportion plus the 95% confidence interval (overall and for each treatment group). The 28-day mortality will be compared between treatment groups using a chi-square or Fisher's exact test. The potential association of each of the categorical prognostic factors (gender, race, high or low Apache score, clinical center) with mortality will also be evaluated using a Chi-square test or Fisher's exact test. Baseline continuous prognostic factors (age, SOFA score, blood glucose) will be compared by treatment group using the Wilcoxon rank-sum test. Odds ratios will be calculated to measure the degree of association. All statistical tests will be 2-sided. Factors significant to at least a value of $P \leq 0.20$ in the univariable analyses will be used in multivariable logistic regression analyses. Forward and backward stepwise selection will be used if necessary to choose prognostic variables for a multivariable logistic regression model. The odds ratio and its 95% confidence interval will be calculated for each factor in the presence of others in the final model.

Days on mechanical ventilation, length of ICU stay and hospital length of stay will be summarized with percentiles (25th, 50th and 75th) and the median absolute deviation. These secondary outcomes will be compared between the 3 treatment groups using the Kruskal-Wallis test. Repeated-measures analyses of daily SOFA scores and laboratory measures such as blood glucose will be analyzed with a means model with SAS Proc Mixed (version 9, mixed linear models) providing separate estimates of the means by time on study (days 0, 3, 7, 14, 21, and 28) and treatment group (energy dose: 0.6, 1.0 and 1.3 x REE). An unstructured variance-covariance form among the repeated measurements will be assumed for each outcome and estimates of the standard errors of parameters will be used to perform statistical tests and construct 95% confidence intervals. T-tests will be used to compare the pairwise differences between the model-based treatment means (least-squares means) at each time point. Statistical tests will be 2-sided. The model-based means are unbiased with unbalanced and missing data, so long as the missing data are non-informative (missing at random). A dropout process is assumed to be missing at random if; conditional on the observed data, the dropout is independent of the unobserved measurements.

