For Aim 2: The agreement between the study entry HBE and the initial REE, as well as the mean daily serial MREE by metabolic cart, will be summarized using graphical methods and by calculating the 95% limits of agreement estimated by the mean difference ± 1.96 standard deviation of the differences. Bland and Altman (1999)⁶³ extend the limits of agreement approach to data with repeated measurements (i.e., serial REE measurements). To investigate whether the relationship between mean daily serial REE and entry HBE is altered by the mean daily caloric dose administered, regression methods will be used (i.e., analysis of covariance, ANCOVA). ANCOVA analyses will also be stratified by location (ICU versus the floor).

For Aim 3: The data processing will be performed as follows: 1) Feature detection conducted by systematic re-extraction with multiple parameter settings that optimize sensitivity and reliability; 2) Sample quality and feature consistency evaluation; 3) Feature overlap detection between datasets; 4) Statistical analysis includes false discovery rate (FDR; typically with $q=0.05$) to identify significantly different features between the two groups while correcting for multiple comparisons; hierarchical cluster analysis (HCA) to visualize differences between groups as

well as between time points and to identify clusters of highly correlated features that can be mapped to biological pathways; 5) Characterization of features and biological pathways utilizing multiple chemical databases (KEGG) metabolic pathways

(http://www.genome.jp/kegg/tool/color_pathway.html), MetaCore (www.genego.com; Carlsbad, CA), and MetaCyc (<http://www.metacyc.org>).⁶⁹ We will utilize Metaboanalyst 2.0⁷⁰ for the time series analysis to detect metabolic changes throughout the study period and two-way ANOVA to determine the impact of varying energy doses on global metabolomics patterns. Once important features have been identified, we have the ability to positively identify the chemical names of known metabolites by MS/MS analysis.

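### Aim 3 plans a two-way ANOVA of energy dose on serial metabolomic samples and names no patient term; run in its ordinary form, its dose and dose-by-time tests would both be invalid

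*Combined protocol and SAP*

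**What the plan says.** The design has three parallel dose groups: "A total of 60 patients will be studied (20 per energy dose group" (Abstract). Under High-resolution metabolomics analysis, "Plasma samples will be obtained at baseline and on days 3, 7, 14, 21 and 28 after entry", so a patient contributes up to six samples. The blood-volume sentence in Data Collection, item C, lists only five draws: "A total of 28 mL of blood will be drawn at baseline and days 7, 14, 21 and 28 of study". Each sample is run three times: "Samples will be analyzed in triplicate with a Thermo LTQ-Velos Orbitrap high-resolution mass spectrometer". Whether the triplicates are averaged before analysis is not stated.

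Statistical Analysis, For Aim 3, then names two longitudinal analyses in one sentence. The one that concerns dose is given as "two-way ANOVA to determine the impact of varying energy doses on global metabolomics patterns". Its companion relies on the MetaboAnalyst 2.0 software, chosen "for the time series analysis to detect metabolic changes throughout the study period". For the ANOVA, the second factor, the error term and any patient term are not given. FDR control, typically at q=0.05, is described as a step "to identify significantly different features between the two groups while correcting for multiple comparisons", although the trial has three dose groups.

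Elsewhere the same section does specify how repeated measurements on one patient are handled:

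- Infection counts (For Aim 1): GEE with an exchangeable within-subject correlation.
- SOFA and laboratory measures such as glucose (For Aim 1): a mixed model on study days 0, 3, 7, 14, 21 and 28, in which "An unstructured variance-covariance form among the repeated measurements will be assumed for each outcome".
- Microbiome (last paragraph of the section): a repeated-measures mixed linear model.

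**The concern.** Dose varies between patients, so the test of dose has to be judged against variation between patients. An ordinary two-way dose-by-time ANOVA judges it against a pooled within-cell residual and counts up to 60 × 6 = 360 samples as if each came from a different patient. Samples from one patient resemble each other, so the dose mean square is larger than that residual even when dose does nothing. The dose-by-time mean square is smaller than the residual, so that test errs in the other direction.

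The effect of dose on metabolomic patterns is the substance of Aim 3 and of Hypothesis 2, and the Background says that later nutritional strategies could build on the metabolites found. A feature list from an ordinary ANOVA would contain too many spurious overall dose effects and too few genuine divergences over time. FDR control takes the P values as given, so it cannot correct either fault.

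**Working it through.** The plan states no error rate, power or within-patient correlation for this analysis, so there is no figure to reproduce.

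**Inputs from the documents.** Number of groups g = 3; patients per group n = 20; samples per patient m up to 6 (5 if the blood-volume sentence is taken literally).

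**Assumptions.** Nominal per-feature level 0.05; equal correlation ρ between any two samples of a patient (compound symmetry); total variance 1; no true dose effect; complete sampling unless stated.

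**Expected mean squares.**

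- Dose: 1 + (m − 1)ρ.
- Pooled within-cell residual: {[1 + (m − 1)ρ] + (m − 1)(1 − ρ)} / m = 1, on g(n − 1)m = 3 × 19 × 6 = 342 degrees of freedom. The correct between-patient error has only 3 × 19 = 57.
- Dose-by-time: 1 − ρ.

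The ordinary F ratio for dose is therefore centred near 1 + (m − 1)ρ instead of 1, and the interaction ratio near 1 − ρ.

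**Check by hand.** With 2 numerator degrees of freedom and a large denominator, the chance of exceeding the critical value is about exp{−F_crit / [1 + (m − 1)ρ]}, where F_crit is about 3.02 for 2 and 342 degrees of freedom.

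- ρ = 0.1: exp(−3.02/1.5) = 0.13
- ρ = 0.2: exp(−3.02/2.0) = 0.22
- ρ = 0.5: exp(−3.02/3.5) = 0.42
- ρ = 0.7: exp(−3.02/4.5) = 0.51

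**Simulated type I error of the ordinary ANOVA (400,000 draws per setting).**

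| ρ | Dose, m = 6 | Dose, m = 5 | Dose, m = 4 | Dose-by-time, m = 6 |
|---|---|---|---|---|
| 0 | 0.049 | 0.049 | 0.050 | 0.050 |
| 0.05 | 0.090 | 0.081 | 0.073 | 0.038 |
| 0.1 | 0.134 | 0.116 | 0.098 | 0.028 |
| 0.2 | 0.222 | 0.188 | 0.152 | 0.012 |
| 0.3 | 0.300 | 0.255 | 0.205 | 0.0045 |
| 0.5 | 0.423 | 0.367 | 0.300 | 0.0002 |
| 0.7 | 0.513 | 0.453 | 0.379 | < 0.0001 |

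**Sensitivity of the dose test (4,000 simulated data sets per setting).**

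- Assumed attrition, mean 4.3 samples per patient: 0.109, 0.247, 0.358 and 0.450 at ρ = 0.1, 0.3, 0.5 and 0.7.
- Correlation that decays over days, complete data: 0.160, 0.320 and 0.455 for half-lives of 3, 7 and 14 days.
- Patient as the unit of error (ANOVA on patient means), complete data: 0.047 to 0.054 for ρ from 0.1 to 0.8, which is nominal within simulation error.

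**Effect on the feature list, for illustration only.** Assume 2,000 independent features, complete six-sample data and Benjamini-Hochberg at q = 0.05.

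- 5% of features truly affected, with steps of 0.6 SD between adjacent doses: the false share of the list is about 60%, 75% and 85% at ρ = 0.2, 0.3 and 0.5. With the patient-level test it is 4% to 5%.
- 20% truly affected, with shifts of plus or minus 0.5 SD: about 32% to 64% for ρ from 0.2 to 0.7.
- 30% truly affected, same shifts: about 24% to 52%.

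In all of these settings the false share exceeds the intended 5%, but its size depends on inputs that the documents do not contain.

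**The case against.** The strongest reply is that the plan is silent and does not choose independence. A two-way ANOVA with time as a within-subject factor is still a two-way ANOVA, and it does not have this fault. The High-resolution metabolomics section also speaks of comparing profiles at the individual sampling times. Separate analyses at each time use one sample per patient and carry no inflation. The authors handle within-patient correlation properly for three other outcomes, which suggests terse wording here. The work is exploratory, in a pilot trial.

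Much of this stands, and it rules out three stronger conclusions that a reader might draw:

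- **That the plan treats the serial samples as independent.** It does not say so. That is one way of carrying out what is written.
- **That false dose effects rise four- to tenfold.** This needs a correlation of about 0.2 to 0.7 and all six samples from every patient. With six samples the inflation is 1.8-fold at correlation 0.05 and 2.7-fold at 0.1; with fewer samples it is smaller. Full sampling is unlikely in patients whose high morbidity and mortality the protocol itself notes.
- **That the list of dose-related metabolites would be mostly false.** This holds in some of the illustrated settings and not in others.

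The reply does not remove the point. The sentence names a method whose ordinary form gives invalid tests for these data, and the contrast with the other repeated outcomes gives an analyst no reason to add a patient term. Analyses by time point would be valid for dose at each day, but they would not test whether the groups diverge over time, and they are not what the sentence on dose describes.

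**Conclusion.** The point holds conditionally. The two-way ANOVA for the effect of dose on metabolomic features has no stated patient term, and the features are measured up to six times per patient. Run as an ordinary dose-by-time ANOVA, its false-positive rate for the dose main effect would be about 13% to 51% per feature with six samples, and about 10% to 38% with four, against a nominal 5%. The dose-by-time test would fall to about 1% at correlation 0.2 and lower beyond that, at the expense of power to detect divergence over time.

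These figures rest on assumed correlations of 0.1 to 0.7, equal correlation between all pairs of samples, complete sampling and an assumed per-feature level of 0.05. The dose inflation persists under the assumed attrition and under decaying correlation; the interaction result was computed under equal correlation only. The FDR step does not restore validity, but the documents do not allow the false share of the list to be stated. The consequence is confined to Aim 3; the infection endpoint is untouched. It should be corrected before the metabolomic data are analysed.

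**What to change.** Replace the two-way ANOVA in Statistical Analysis, For Aim 3, with a per-feature linear mixed model:

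- Average the triplicate runs first, so that each patient has one value per sampling day.
- Use the post-baseline samples as the response, with dose, time and dose-by-time as fixed effects and the day-0 level as covariate.
- Include a patient random effect, or use the unstructured covariance already planned for SOFA and laboratory measures. Choose one in advance. With five post-baseline days an unstructured matrix has 5 × 6 / 2 = 15 parameters per feature, so state the fallback for features where it does not converge.
- Apply the FDR to the dose and dose-by-time P values across the three groups, and say whether these form one family or two.

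The model also uses incomplete series from patients who die or are discharged, under the missing-at-random assumption that the plan already states for Aim 1. If comparisons at each sampling day are wanted as well, list them separately.

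The cost is modest programming and probably fewer declared features. No visit, sample or treatment changes, and the plan already uses models of this kind for other outcomes.

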cardiac death⁴⁵⁻⁴⁹. Fractal analysis of metabolomic data will allow us to test whether the Hurst exponent is related to clinical outcomes and/or response to nutritional interventions in the ICU patients we propose to study.

Emerging data strongly suggest that microbes of the intestine (the microbiota) play a key role in host metabolism, immune/inflammatory processes and disease pathophysiology⁵⁰⁻⁵². The intestinal microbiome (genome of the gut microbiota) is shaped by both environment (e.g. diet) and host genetics; and, vice versa, the gut microbiota itself appears to regulate a wide spectrum of host immune, inflammatory and metabolic responses⁵³. **Human data on the impact of nutrition support during critical illness on the gut microbiome are limited.**

Despite limited evidence, there is a suspected interplay between critical illness and the gut microbiome, which warrants further exploration in the setting of nutrition support⁵⁴⁻⁵⁸. Nelson et al utilized 16S rRNA pyrosequencing to characterize stool of hospitalized patients and observed perturbations in gut microbiota following infection⁵⁹. It is acknowledged that the microbiome plays an integral role in health maintenance, and that modifications of the gut microorganisms may influence outcomes in critically ill patients.

Hypothesis:

- 1) Adequate energy administration (defined as 1.3 x REE) will result in a lower 28-day total hospital-acquired infection rate compared with ICU patients receiving lower energy doses.
- 2) Differences in energy intake will result in global changes in metabolic patterns that themselves are associated with clinical outcomes in the ICU patients studied.

Specific Aims:

- 1) To perform a controlled, double-blind, prospective, randomized, parallel group, intent-to-treat Phase II clinical trial to test the efficacy of three specific energy doses [0.6, 1.0 and 1.3 x measured REE (metabolic cart), respectively], given for 28 consecutive days during the ICU course, on 28-day total hospital-acquired infections (primary endpoint), BSI, and other important clinical outcomes in medical/surgical ICU patients requiring specialized parenteral ± enteral feeding.
- 2) In Aim 1 subjects to: a) examine the impact of cumulative and mean daily 28-day energy deficits [energy intake-measured REE] on clinical outcome endpoints; and b) to estimate the agreement for REE as determined by the HBE and the measured REE across different energy doses.

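### The metabolomic dose test for Hypothesis 2 states no adjustment for the baseline sample; using that sample as a covariate would raise power, modestly or substantially depending on a correlation the plan does not give

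*Combined protocol and SAP*

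**What the plan says.** Hypothesis 2 reads: "Differences in energy intake will result in global changes in metabolic patterns that themselves are associated with clinical outcomes in the ICU patients studied". The sampling schedule, under High-resolution metabolomics analysis, is: "Plasma samples will be obtained at baseline and on days 3, 7, 14, 21 and 28 after entry". The blood-sampling item under Data Collection has the first sample "drawn between 0800 and 1000 h. at the baseline day", and the nutrition support section records study intake from day 1. The first sample therefore precedes study feeding.

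Under Statistical Analysis, For Aim 3, the dose test is one clause: a "two-way ANOVA to determine the impact of varying energy doses on global metabolomics patterns", placed next to a time series analysis in the same software. The clause does not name the factors, list the time levels, say whether the main effect or the interaction answers the dose question, or mention baseline. The same section plans "false discovery rate (FDR; typically with $q=0.05$) to identify significantly different features between the two groups". The metabolomics section also announces a second kind of comparison: "Metabolomic profiles at the specific analysis time-points will be compared to compare subjects: 1) within the three study energy doses".

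No baseline covariate or change from baseline is planned for metabolomics. Elsewhere the plan does address baseline. The microbiome paragraph uses change from baseline to handle differences between individuals. The mixed model for SOFA and laboratory values under Aim 1 lists day 0 as a time level.

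**The concern.** Randomisation makes the arms equal in expectation in a sample taken before study feeding. That sample carries no dose effect, but it does carry information about each patient's usual level of a feature. If it enters a dose-by-time ANOVA as one more time level, two things happen to the dose main effect: it is averaged over a visit where it is zero by design, and the patient-to-patient variation that the baseline value could remove stays in the error. Testing dose-by-time instead avoids the averaging but spreads the signal over 10 degrees of freedom.

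At stake is sensitivity for a stated hypothesis in a small pilot ("A total of 60 patients will be studied (20 per energy dose group" in the Abstract), with FDR control on top. Features missed here would not be carried into the larger trials that the pilot is meant to inform.

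**Working it through.** The plan gives no metabolomic power, effect size, SD or correlation, so there is no figure to reproduce. The calculation compares analyses under stated assumptions.

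**From the documents.** Three arms of 20; six samples, one before study feeding and five after.

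**Assumed.** SD 1 at every visit; the same correlation rho between any two visits (0.3, 0.5, 0.7, with 0 as a limit); complete samples; shifts of -0.3, 0 and +0.3 SD across the three doses, constant from day 3 to day 28 and absent at baseline; single-feature alpha 0.05.

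**Common term.** n × sum of squared shifts = 20 × (0.09 + 0 + 0.09) = 3.6. The noncentrality is 3.6 divided by the effective variance, and power comes from the noncentral F distribution.

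1. *Main effect over six visits, with a patient term.* The patient mean has variance (1 + 5rho)/6 and the effect is multiplied by 5/6. The effective variance is [(1 + 5rho)/6]/(5/6)² = 0.60, 0.84, 1.08. Noncentrality 6.00, 4.29, 3.33; df 2, 57.
2. *Dose-by-time.* Noncentrality 3.6 × (5/6)/(1 - rho) = 4.29, 6.00, 10.00; df 10, 285.
3. *Mean of the five later samples, unadjusted.* Variance (1 + 4rho)/5 = 0.44, 0.60, 0.76. Noncentrality 8.18, 6.00, 4.74; df 2, 57.
4. *The same mean, adjusted for baseline.* Variance (1 + 4rho)/5 - rho² = 0.35, 0.35, 0.27. Noncentrality 10.29, 10.29, 13.33; df 2, 56.

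| Power | rho 0.3 | rho 0.5 | rho 0.7 |
|---|---|---|---|
| Six-visit main effect, patient term | 56% | 42% | 34% |
| Dose-by-time | 22% | 31% | 53% |
| Later samples only, unadjusted | 70% | 56% | 46% |
| Later samples, baseline-adjusted | 80% | 80% | 90% |

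**Variance cut, line 4 against line 1.** 1 - 0.35/0.60 = 42%; 1 - 0.35/0.84 = 58%; 1 - 0.27/1.08 = 75%.

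**Limit at rho 0.** Effective variances 0.24 and 0.20, noncentrality 15 and 18, power 93% against 97%.

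**Where the loss comes from.** At rho 0.5, dropping baseline from the average moves power from 42% to 56%; adding the covariate moves it from 56% to 80%. The missing covariate is the larger part at rho 0.5 and 0.7. At rho 0.3 the two parts are similar (14 and 10 points), and at rho 0 only the dilution remains.

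**Sensitivity.**
- Alpha 0.001 as a stand-in for an FDR threshold, rho 0.5: 6% (main effect) against 29% (adjusted).
- Only two later samples per patient, rho 0.5, alpha 0.05: effective variances [(1 + 2 × 0.5)/3]/(2/3)² = 1.50 and (1 + 0.5)/2 - 0.25 = 0.50, so 25% against 64%.
- Correlation that decays with time (AR(1), 0.3 to 0.7) and a larger effect, 0.8 SD between the extreme doses (simulated): from 95% against 98% to 70% against 91%.
- An effect that grows over time (simulated, with the effect rescaled at each rho): dose-by-time 37%, 53%, 65% against 75%, 75%, 74% adjusted, at rho 0.3, 0.5, 0.7.

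**The case against.** The strongest reply is that the plan does not say what is being criticised. A reader might infer that it specifies baseline as a time level. It does not: the factors are unnamed, and the only place where day 0 is listed as a level concerns SOFA and laboratory values. This stands. What the documents support is that no baseline adjustment is stated and that dose by time is the natural reading, given the time series analysis beside it.

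Second, the power figures include a patient term that the plan does not mention. This also stands. A literal two-way ANOVA that treats all samples as independent would not miss features. In simulation it rejects about 30%, 41% and 50% of the time under the null at rho 0.3, 0.5 and 0.7, and 89%, 88% and 86% of the time with the assumed shifts. Its fault is false positives, which is a separate matter. The efficiency loss described here applies once the test has been made valid.

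Third, the dilution affects only a main effect averaged over all visits. It does not affect the interaction or the comparisons at individual time-points. That is correct, but no baseline adjustment is stated for those either.

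Fourth, the trial is a pilot, Aim 3 is exploratory, and no metabolomic power is claimed. That bears on the weight of the point, not on whether the better analysis is available.

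**Conclusion.** The plan collects a baseline value for each metabolomic feature and states no use for it in the dose test. Under the assumptions above, the baseline-adjusted test has more power than either valid dose-by-time test at every correlation shown. The size of the gain is uncertain. A reader might conclude that the plan gives up about half its power, but that describes the main effect only near rho 0.5 (42% against 80%). The loss is 93% against 97% at rho 0 and 34% against 90% at rho 0.7, and the documents give no correlation to choose between these. The figures also rest on equal correlation, complete samples to day 28 and a constant effect, which may not hold in patients this ill.

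Nor should the baseline sample be taken as unfed. It precedes study feeding, but patients may enter up to 168 hours after ICU admission, and nothing says that they received no nutrition before then.

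This is a cheap efficiency gain for an exploratory aim. No stated figure is wrong.

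**What to change.** Name the factors and the role of baseline in the Aim 3 analysis text. For each feature, fit a mixed model with a patient term to log intensities at days 3, 7, 14, 21 and 28, with dose arm, day and the patient's log baseline intensity as a covariate. Test the dose effect averaged over those days, then apply the planned FDR at q = 0.05.

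The cost is a few lines of SAP text and a different model call; no further samples are needed. The downside is that a patient without a baseline sample drops out of this test unless a constrained-baseline model is used, in which baseline is an outcome with a common mean across arms. The choice should be written down before the data are analysed.
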